### **1.4. Study Endpoints**

#### **1.4.1. Primary Endpoints**

The following safety parameters will be recorded at regular intervals during the study:

- Adverse Events (AEs) (by type, severity, and relatedness) at each visit.
- Changes in safety clinical laboratory testing and vital signs at each visit.
- Changes in electrocardiograms (ECGs) at Months 1, 3, 6, 9, and 12.

#### **1.4.2. Secondary Endpoint**

There are no secondary endpoints defined for this study

#### **1.4.3. Exploratory Endpoints**

The exploratory endpoints are:

- Proportion of patients with scores of clear or almost clear (0 or 1) of the reference lesion on the Investigator Global Assessment: NL (IGA:NL) Activity Scale at Months 1, 2, 3, 4, 5, 6, 9, and 12.
- Proportion of patients with  $\geq$  1-point decrease in IGA:NL Activity score of the reference lesion at Months 1, 2, 3, 4, 5, 6, 9, and 12.
- Proportion of patients with  $\geq$  2-point decrease in IGA:NL Activity score of the reference lesion at Months 1, 2, 3, 4, 5, 6, 9, and 12.

- Proportion of patients with  $\geq$  1-point decrease in the Color score on the Necrobiosis Lipoidica Color and Ulcer Scale (NLCUS) of the reference lesion at Months 1, 2, 3, 4, 5, 6, 9, and 12.
- Change from Baseline in Physician Global Assessment (PGA) score at Months 1, 2, 3, 4, 5, 6, 9, and 12.
- Percent change from Baseline in reference lesion surface area of inflammation/erythema based on Investigator measurement at Months 1, 2, 3, 4, 5, 6, 9, and 12.
- Percent change from Baseline in total lesion(s) surface area of inflammation/erythema based on Investigator measurement at Months 1, 2, 3, 4, 5, 6, 9, and 12.
- Percent change from Baseline in reference lesion surface area of inflammation/erythema based on photograph at Months 1, 2, 3, 4, 5, 6, 9, and 12.
- Change from Baseline in Dermatology Quality of Life Index (DLQI) score at Months 1, 2, 3, 4, 5, 6, 9, and 12.
- Change from Baseline in Skindex-29 score at Months 1, 2, 3, 4, 5, 6, 9, and 12.
- Change from Baseline in Patient Global Assessment (PtGA) visual analog scale (VAS) score at Months 1, 2, 3, 4, 5, 6, 9, and 12.
- Time to obtaining scores of clear or almost clear (0 or 1) of reference lesion on the IGA:NL Activity scale.
- Incidence of new ulceration (defined as a site with no previous ulceration) at Months 1, 2, 3, 4, 5, 6, 9, and 12.
- Time to new ulceration.

Patients with ulceration at Baseline only:

- Proportion of patients with  $\geq$  1-point decrease in the Ulcer score on the Necrobiosis Lipoidica Color and Ulcer Scale (NLCUS) of the reference lesion at Months 1, 2, 3, 4, 5, 6, 9, and 12.
- Percent change from Baseline in reference ulcer surface area based on Investigator measurement at Months 1, 2, 3, 4, 5, 6, 9, and 12.
- Percent change from Baseline in total ulcer surface area based on Investigator measurement at Months 1, 2, 3, 4, 5, 6, 9, and 12.
- Percent change from Baseline in reference ulcer surface area based on photograph at Months 1, 2, 3, 4, 5, 6, 9, and 12.
- Incidence of complete wound closure of reference ulcer (defined as skin re-epithelialization without draining or dressing requirements confirmed at two consecutive study visits at least 2 weeks apart) at Months 2, 3, 4, 5, 6, 9, and 12.
- Time to complete wound closure of reference ulcer.
- Incidence of recurrence of reference ulcer after complete wound closure at Months 3, 4, 5, 6, 9, and 12.
- Time to recurrence of reference ulcer after complete wound closure.
- Change from Baseline in reference ulcer volume based on 3D scanning at Months 1, 2, 3, 4, 5, 6, 9, and 12.

Exploratory Serum Biomarkers:

- Change from baseline in TNF- $\alpha$ , IFN- $\gamma$ , IL-1 $\beta$ , IL-6, IL-12, IL-17, and MCP-1 at Months 1, 3, 6, 9 and 12.
- Change from baseline in C-peptide levels at Months 1, 3, 6, 9 and 12.

## **2. Detailed Statistical Methods**

### **2.1. General Statistical Methods**

The statistical analysis of the data obtained from this study will be the responsibility of the study biostatistician. If, after the study has begun, changes are made to the statistical analysis plan, these deviations will be listed in the Documentation of Statistical Decisions document, along with an explanation as to why they occurred.

Continuous data will be summarized using descriptive statistics (number, mean, median, standard deviation, minimum, and maximum values). Categorical data will be summarized using frequency tables (frequency and percent).

If at the end of the study the Efficacy Population and the Per Protocol Population include the same patients, then only table and figure output for the Efficacy Population will be produced.

### **2.2. Study Populations**

#### **Safety Population**

All patients enrolled in the study who received at least 1 dose of treatment.

#### **Efficacy Population (mITT)**

All patients enrolled in the study who received at least 1 dose of treatment and have at least 1 post-baseline efficacy assessment.

#### **Per-Protocol Population (PP)**

All patients enrolled in the study who received at least one dose of study treatment, have at least 1 post-baseline efficacy assessment, and did not have a major protocol violation.

#### **Biomarker Population**

All patients enrolled in the study who received at least 1 dose of treatment, participated in biomarker evaluations, and have appropriate samples available for analysis.

### **2.3. Disposition of Patients**

The number and percentage of patients entering, discontinuing or completing the study will be presented. Reasons for withdrawal pre- and post-randomization will also be summarized.

## **2.4. Demographics and Patient Baseline Characteristics**

Demographic data (age, sex, race, and ethnicity), baseline characteristics (age, weight, height, and body mass index), and general medical history will be summarized by means of descriptive statistics or frequency tables.

## **2.5. Study Drug Accountability**

Treatment compliance will be assessed via tablet counts. Patients will be dispensed kits of study medication and dose and frequency will be recorded starting at Visit2/Day 0 (Baseline) and at every clinic visit starting at Month 1/Day 28 through Month 11/Day 270. The number of tablets returned will be captured starting at Month 1/Day 28 and repeated at every clinic visit through Month 12/Day 360.

The actual number of tablets taken, expected number of tablets taken based on the dose and frequency assigned, and percentage of tablets taken will be listed and summarized by descriptive statistics (n, mean, median, standard deviation, minimum and maximum) by clinic visit and overall.

The dose and frequency of dosage will be listed and summarized in frequency tables by clinic visit.

Actual number of tablets taken will be defined as the difference between the number of tablets dispensed and the number of tablets returned for each clinic visit and overall. Expected number of tablets number of tablets will be calculated as the maximum number of tablets based on the number of days between dispensation and collection of study drug, and the expected study dose and regimen for that particular study month. The percentage of tablets taken will be the ratio of actual number of tablets taken and expected number of tablets taken multiplied by 100.

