## 9.2.2.2. Day 7 and Day 14 (Phone Checks, +/- 1 day)

The site will call the patient on Day 7 and Day 14 to assess for any adverse events or tolerability issues the patient may have experienced since starting dosing. A review of systems will be discussed and any changes in concomitant medications will also be solicited.

- If a patient reports satisfactory tolerability to study medication on the Day 7 Safety Check-in, they will be instructed to increase their morning dose to 3 tablets and their evening dose to 3 tablets.
- If a patient reports tolerability issues, an additional week of dosing with the morning dose of 1 tablet and evening dose of 1 tablet may be performed.
- Patients who are unable to tolerate even the single tablet after 2 weeks of dosing are to be discontinued from the study.

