### 11. TREATMENT OF PATIENTS

### 11.1. Description of Study Drug

PCS499 is a stable, optically active, white-crystalline solid with the chemical name (S)-1-(4,4,6,6,6-pentadeutero-5-hydroxyhexyl)-3,7-dimethyl-1H-purine-2,6(3H,7H)-dione. The structural formula is provided in Figure 1 .

Date: 02 November 2018

Figure 1: Structural Formula for PCS499

$$D_3C \xrightarrow{\stackrel{OH}{\downarrow}} D \xrightarrow{O} N \xrightarrow{N} N$$

The molecular formula is C13H15D5N4O3.

The dosage form is a white tablet containing 300 mg of PCS499. The inactive ingredients are hydroxypropylmethylcellulose (HPMC), silicon dioxide, and magnesium stearate.

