#### 12.5. Administration

All patients will take PCS499 300 mg BID with food for 1 week. Beginning at Week 2, patients will commence administration of twice daily dosing of three PCS499 300 mg tablets (900 mg BID) with food. Patients will continue at their assigned dose for the remainder of the study.

Safety and tolerability will be assessed throughout study and the following steps may be taken:

• During the dosing period, if a patient receiving PCS499 900 mg BID experiences unacceptable toxicity (i.e., non-transient, moderate to severe limitation in activity) that is deemed by the Investigator to be related to study drug, his/her dose will be changed to PCS499 600 mg TID with food at the discretion of the Investigator in consultation with the Medical Monitor. If this dose is not tolerated, the dose will be further reduced to PCS499 600 mg BID with food at the discretion of the Investigator in consultation with the Medical Monitor. If 4 out of the first 6 patients dosed in this study require dose modification or discontinue from the study due to a drug-related adverse event within 1 month of dosing, consideration will be made to change the starting dose to 600 mg TID with food for all subsequent patients. If clinically indicated at any time during the study, study medication will be discontinued. However, patients will not be discontinued from the study due to cessation of study drug.

All changes in medication administration will also be noted in the eCRF.

Each kit will be clearly marked with dosage instructions.

Each subject's medication will be packaged for dispensing as described in the study manual.

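### SAP 2.5 defines expected tablets in two ways, and its calculation rule can understate compliance for fully adherent patients

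*SAP*

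**What the plan says.** SAP 2.5 reports compliance as tablets taken (dispensed minus returned) over tablets expected, times 100, by clinic visit and overall. The denominator is described twice.

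- The reporting paragraph has "expected number of tablets taken based on the dose and frequency assigned".
- The calculation paragraph has "Expected number of tablets number of tablets will be calculated as the maximum number of tablets based on the number of days". That sentence then runs the days from dispensing to collection and adds a second input, the dose and regimen expected in the study month concerned.

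The SAP's Document History lists this definition among the version 2.0 updates.

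The Protocol lets the daily count change within and between months:

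- Section 11.1: "The dosage form is a white tablet containing 300 mg of PCS499".
- Section 12.5, lead-in: "All patients will take PCS499 300 mg BID with food for 1 week", followed by "twice daily dosing of three PCS499 300 mg tablets (900 mg BID) with food".
- Section 9.2.2.2, where tolerability is a problem at the phone check: "an additional week of dosing with the morning dose of 1 tablet and evening dose of 1 tablet may be performed".
- Section 12.5, first modification step: "his/her dose will be changed to PCS499 600 mg TID with food at the discretion of the Investigator". A further step goes to 600 mg BID.
- Section 12.5 also allows study drug to be stopped while the patient remains in the study, and section 15.1.4.1 requires interruption after a positive urine pregnancy test.

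On records, Protocol 12.5 states: "All changes in medication administration will also be noted in the eCRF".

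**The concern.** If the assigned dose were the whole rule, the word maximum would add nothing. A programmer who gives it meaning could count the full 6 tablets on every day. The calculation sentence also speaks of one dose and regimen per study month, yet Month 1 holds two dose levels for every patient by design. It ends the count at collection of the drug, with no provision for a stop or an interruption before that.

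Apart from the planned lead-in week, which everyone has, the patients exposed to this are those with a longer lead-in, a reduction to 600 mg BID, or a stop. In a study of safety and tolerability, a patient who followed instructions exactly could then appear in the compliance tables as having missed a third of the tablets.

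**Working it through.** The documents state no compliance figure, so there is none to reproduce. The check is tablet arithmetic for a patient who takes every tablet as directed.

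**Inputs** (Protocol 9.2.2.2, 11.1 and 12.5), at 300 mg per tablet:
- lead-in, 300 mg BID: 2 tablets/day, for 7 days or, if extended, 14
- 900 mg BID: 6 tablets/day
- 600 mg TID: 6 tablets/day
- 600 mg BID: 4 tablets/day
- first accountability interval: Day 0 to Day 28, ±3 days (Protocol 9.2.2.3)

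**Formula:** percent = 100 × (sum over days of tablets taken) / (tablets expected).

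Three denominators fit some part of the SAP wording: (a) 6 tablets on every day; (b) the planned schedule, 2/day for 7 days and then 6/day; (c) the dose assigned to the patient on each day.

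| Adherent patient | Taken | (a) | (b) | (c) |
|---|---|---|---|---|
| Month 1, 28 days, 1-week lead-in | 7×2 + 21×6 = 140 | 140/168 = 83.3% | 140/140 = 100% | 100% |
| Month 1, 28 days, 2-week lead-in | 14×2 + 14×6 = 112 | 112/168 = 66.7% | 112/140 = 80.0% | 100% |
| Later 30-day interval, 600 mg TID | 30×6 = 180 | 180/180 = 100% | 100% | 100% |
| Later 30-day interval, 600 mg BID | 30×4 = 120 | 120/180 = 66.7% | 120/180 = 66.7% | 100% |

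**Visit window, denominator (a).** At 25 days the Month 1 figures are 122/150 = 81.3% and 94/150 = 62.7%. At 31 days they are 158/186 = 84.9% and 130/186 = 69.9%.

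**Change between visits.** If the dose recorded at dispensing is carried through the interval, a patient moved to 600 mg BID halfway through 30 days takes 15×6 + 15×4 = 150 of 180, or 83.3%.

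**Drug stopped before collection.** As an illustration, a patient on 6 tablets/day who is told to stop halfway through a 30-day interval takes 15×6 = 90. Counting all days to collection gives 90/180 = 50%. This arises whichever daily dose is used for the month, because the off-drug days stay in the denominator.

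**Overall figure, denominator (a):**
- Lead-in only, 180 days: (14 + 173×6)/1080 = 1052/1080 = 97.4% with one week; (28 + 166×6)/1080 = 1024/1080 = 94.8% with two.
- Lead-in only, 360 days: 2132/2160 = 98.7% and 2104/2160 = 97.4%.
- 600 mg BID from Day 28 after a one-week lead-in: (140 + 152×4)/1080 = 748/1080 = 69.3% over 180 days; (140 + 332×4)/2160 = 1468/2160 = 68.0% over 360 days.

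**Effect on a mean.** With 12 patients, one reading of 66.7% in place of 100% lowers the mean by 33.3/12 = 2.8 points.

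**The case against.** The strongest reply is that the text does not commit the analyst to 6 tablets on every day. The calculation sentence goes on to name the dose and regimen of the month, and the reporting paragraph speaks of the assigned dose. Maximum may mean no more than the full count possible at that dose over the elapsed days. Dose and frequency are recorded at dispensing, and the table shells, which might settle the matter, are in a separate file. This stands. A reader might infer that adherent patients will be reported as 67% to 83% compliant; the documents support only that they could be.

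Three other inferences also go too far.

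- *Every dose-modified patient is mis-scored.* The first step, 600 mg TID, leaves the daily count at 6. Among the dose changes, only 600 mg BID alters it.
- *Exposure or the primary endpoints are distorted.* Tablets actually taken are dispensed minus returned and are summarised on their own. Dose and frequency are tabulated by visit, and SAP 2.9.1 has rows for adverse events leading to dose change and to withdrawal of drug. Compliance is not a primary endpoint.
- *Analysis populations change.* The SAP states no compliance cut-off for any population or endpoint.

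The reply does not remove the inconsistency. The calculation sentence gives no method for a month with two doses, and its interval, as written, includes days after a stop.

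**Conclusion.** The definition in SAP 2.5 is inconsistent and incomplete, and read literally it can understate compliance in patients who took everything they were told to take. In Month 1 the figure is 83% or 67% if full dose is assumed throughout, and 100% or 80% if the planned titration is the standard. It is 67% per interval on 600 mg BID if the planned dose is used in place of the modified one. It falls below 100% whenever drug is stopped and the days to collection are still counted. A day-by-day count of the assigned dose gives 100% in each of the dosing cases tabulated.

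The reach is narrow: tables 14.1.5.1 to 14.1.5.3 and listing 16.2.5, all descriptive. Titration alone hardly moves the overall percentage; a lasting reduction to 600 mg BID does. All figures assume perfect adherence and accurate tablet returns. How many patients would be affected by an extended lead-in, a reduction or a stop cannot be known from the plan. The point is worth correcting as a matter of definition and does not threaten the study's conclusions.

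**What to change.** In SAP 2.5, delete the word maximum and use one definition in both paragraphs. Expected tablets are the sum, over days, of the tablets per day assigned to that patient on that day, taken from the recorded dose changes. The sum runs from dispensing to the earlier of return or the recorded stop date and leaves out directed interruptions. This covers the lead-in, the extra week, changes between visits and early stops with no special cases.

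A separate row for dose reductions is optional, since dose and frequency are already tabulated by visit.

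The cost is one sentence and one derivation. The Protocol already requires changes in administration to be entered in the eCRF, so no new data are needed.

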## **2.6. Prior and Concomitant Medications**

Prior and concomitant medications will be identified using the September 2018 release version of the World Health Organization (WHO) Drug dictionary.

Concomitant medications are defined as any medication taken by the patient during the course of the study following the first dose.

Prior medications are defined as any medication taken by the patient within 30 days of their first dose of study medication.

[Section 2.15](#) describes the imputation rules for partial dates. All medications will be presented in a data listing and summarized by frequency counts.

## **2.7. Pregnancy Test**

The results of the pregnancy tests will be listed separately from hematology and urinalysis laboratory results. A serum pregnancy test will be administered at the screening visit and urine pregnancy tests will be administered at subsequent visits.

## **2.8. Protocol Deviations**

Deviations from the protocol including violations of inclusion/exclusion criteria will be listed and summarized.

## **2.9. Safety Evaluations**

All safety summaries will be presented for the Safety Population.

### **2.9.1. Adverse Events**

Adverse events (AEs) will be coded using the Medical Dictionary for Regulatory Activities (MedDRA) version 21.1.

AEs occurring on or before Visit 2/Day 0 (Baseline) prior to drug administration will be regarded as “pre-treatment” and will not be included in the treatment emergent AE tabulations.

Treatment Emergent Adverse Events (TEAEs) are defined as any AE that starts or increases in severity after drug administration at Visit 2/Day 0 and will be summarized.

Listings of all AEs will be provided and separately by:

- Treatment Emergent AEs
- AEs leading to discontinuation of study
- Serious AEs

An overall summary table will be provided showing the number and percentage of patients with any:

- Pre-Treatment AEs
- TEAE
- Severe TEAE
- Serious TEAE
- Drug-related TEAE
- Drug-related severe TEAE
- Drug-related serious TEAE
- TEAE leading to withdrawal of study drug
- TEAE leading to change in study drug dose
- TEAE with outcome death

The number of reported AEs will also be shown in this summary table.

Summary tables for the following will also be presented:

- Summary of TEAEs by Body System and Preferred term,

- Summary of TEAEs by Severity,
  - If a patient has reported the same treatment emergent adverse event multiple times then the adverse event with the highest severity will be summarized.
- Summary of Drug-related TEAEs, and
- Summary of Drug-related TEAEs by Severity.
  - If a patient has reported the same drug-related treatment emergent adverse event multiple times, then the adverse event with the highest severity will be summarized.

Inferential statistical analysis comparing the AE data between active and placebo is not planned.

### **2.9.2. Laboratory Parameters**

Clinical Safety Laboratory assessments will include hematology, chemistry and urinalysis, coagulation, and HgbA1c. Screening panels will include virus serology (HIV, hepatitis B and C, and TB) and FSH (to confirm post-menopausal status).

Observed values of continuous safety laboratory parameters and corresponding changes from baseline will be summarized by descriptive statistics (n, mean, median, standard deviation, minimum and maximum) by visit. Categorical safety laboratory parameters will be summarized by frequency tables.

A clinically significant change from baseline (Visit 2/Day 0) will be recorded as an AE if deemed appropriate by the Investigator.

All laboratory outcomes will be listed.

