#### 9.2.3.4. Unscheduled Visits

All attempts should be made to keep a patient on the study schedule. Unscheduled visits may be necessary to repeat testing following abnormal laboratory results, follow-up on adverse events or for other reasons, as warranted. Procedures that may be performed at the Unscheduled visit are as follows:

- Vital signs
- Physical exam
- Skin/ulcer exam
- 12-lead ECG
- Blood and/or urine collection for safety testing.

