#### 10.3. Patient Withdrawal Criteria

The intent of this study is to follow all subjects until study termination unless the subject withdraws consent. Patients will be informed that they have the right to withdraw from the study

at any time for any reason without prejudice to their medical care. The Investigator also has the right to withdraw patients from the study if it is in their best interest. Patients may be withdrawn from the study if they:

- Have entered the study in violation of the protocol
- Require use of a prohibited concomitant medication
- Experience an AE that warrants premature withdrawal

All treated patients should be followed according to the Schedule of Assessments. All patients, even those who are withdrawn prematurely, should have all evaluations for the Month 12/ET Visit performed, if possible. All procedures required should be documented in the electronic case report form (eCRF). For all patients who withdraw prematurely, the Investigator will indicate one of the following reasons for withdrawal on the eCRF:

- Adverse event (AE)
- Death
- Protocol violation
- Lost to follow-up
- Patient's decision
- Other (reason to be specified by the Investigator)

In case of patients' withdrawal from the study due to an AE, such patients will be closely monitored until the resolution or stabilization of the AE. The Investigator should document the reason for withdrawal in the source documentation and eCRF.

If a patient withdraws participation from the trial early, early withdrawal should be documented by the Investigator (or designee) in the appropriate eCRF pages and source documents when confirmed.

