### 1.2. Study Background/Plan

This is an open-label study that will evaluate the safety of PCS499 for the treatment of necrobiosis lipoidica (NL) and will inform the design of future studies. The study will consist of a 6-month treatment period followed by a 6-month extension period. The test article is PCS499 modified release 300mg tablets.

Approximately 12 NL patients (6-9 patients without ulceration and 3-6 patients with ulceration) who also meet other inclusion/exclusion criteria will be enrolled in the study. Patients will be administered PCS499 900 mg BID. Primary safety and exploratory efficacy analysis will be performed after the last patient completes the 6-month visit. Patients will have the option to continue dosing in an extension period for up to an additional 6 months.

All patients will take PCS499 300 mg BID with food for 1 week beginning at Visit 2/Day 0 (Baseline). At the Visit3/Day 7 and Visit4/Day 14 phone Safety Check-in, patients will be instructed to increase their morning dose to 3 tablets and their evening dose to 3 tablets (PCS499 900 mg BID with food) if satisfactory tolerability to PCS499 300 mg BID is reported. Patients will continue at their assigned dose for the remainder of the study.

During the dosing period, if a patient receiving PCS499 900 mg BID experiences unacceptable toxicity (i.e., non-transient, moderate to severe limitation in activity) that is deemed by the Investigator to be related to study drug, his/her dose will be changed to PCS499 600 mg TID with food at the discretion of the Investigator in consultation with the Medical Monitor. If this dose is not tolerated, the dose will be further reduced to PCS499 600 mg BID with food at the discretion of the Investigator in consultation with the Medical Monitor. If 4 out of the first 6 patients dosed in this study require dose modification or discontinue from the study due to a drug-related adverse event within 1 month of dosing, consideration will be made to change the starting dose to 600 mg TID with food for all subsequent patients. If clinically indicated at any time during the study, study medication will be discontinued. However, patients will not be discontinued from the study due to cessation of study drug. Efficacy and safety data will be collected at regular intervals throughout the course of the study.

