### **1.3. Study Objectives**

#### **1.3.1. Primary Objective**

The primary objective of this study is:

- To evaluate the safety and tolerability profile of PCS499 in patients with Necrobiosis Lipoidica.

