### **2.9.5. Electrocardiogram**

Observed values of continuous ECG parameters and corresponding changes Visit 2/Day 0 will be summarized by descriptive statistics (n, mean, median, standard deviation, minimum and maximum). Results of ECG measurements will be summarized in frequency tables by visit.

A clinically significant change from baseline (Visit 2/Day 0) will be recorded as an AE if deemed appropriate by the Investigator.

Fridericia's formula will be used to derive the QT correction, QTcF parameter. QTcF is defined as the QT interval divided by the cubed root of the RR interval ( $QTcF = QT / \sqrt[3]{RR}$ ).

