## **2.13. Sample Size and Power Considerations**

This study is not powered for statistical significance. No sample size calculations were performed.

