## **2.14. Handling Missing Data**

Listings will be provided for all data. Descriptive statistics will be provided for all planned visits as provided on the Case Report Forms (CRFs). No imputations for missing data will be used in calculations.

Visit windows will not be used in this study. Likewise, unscheduled visits will not be reassigned a visit number based on the visit date.

Dates related to the medications will be imputed using the rules below in an effort to categorize them properly into the summary tables.

Imputing partial or missing start dates:

- If the year is unknown, then the start date will not be imputed. The date will remain missing.
- If the month is unknown, impute the month as January.
- If the day is unknown, impute the day as '01'.

Impute partial or missing stop dates:

- If the year is unknown, then the stop date will not be imputed. The date will remain missing.
- If the month is unknown, impute the month as December.
- If the day is unknown, impute the day to be the last day of the month.

If an imputed stop date is greater than the date of study completion/discontinuation date of the study, then the imputed stop date will be set equal to the date of completion/discontinuation date.

The imputed dates will be stored in the analysis datasets along with the original dates as recorded by the sites.

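### Primary laboratory, vital-sign and ECG changes are summarised only by observed-case statistics at planned visits, with no per-patient worst-value or shift summary and no stated place for unscheduled or early-termination values

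*SAP*

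**What the plan says.** The primary objective in SAP 1.3.1 is "To evaluate the safety and tolerability profile of PCS499 in patients with Necrobiosis Lipoidica". SAP 1.4.1 makes three things primary: adverse events, changes in laboratory tests and vital signs at each visit, and ECG changes at Months 1, 3, 6, 9 and 12.

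For laboratory parameters SAP 2.9.2 says "Observed values of continuous safety laboratory parameters and corresponding changes from baseline will be summarized by descriptive statistics", meaning n, mean, median, SD, minimum and maximum, by visit. SAP 2.9.3 uses the same statistics for vital signs. For ECGs, SAP 2.9.5 says "Observed values of continuous ECG parameters and corresponding changes Visit 2/Day 0 will be summarized by descriptive statistics". Categorical laboratory results and ECG results also get frequency tables, and everything is listed.

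SAP 2.14 adds "Descriptive statistics will be provided for all planned visits as provided on the Case Report Forms (CRFs". It rules out imputation of missing data and visit windows, and it does not reassign unscheduled visits to a planned visit.

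Protocol 9.2.3.4 explains what unscheduled visits are for: "Unscheduled visits may be necessary to repeat testing following abnormal laboratory results, follow-up on adverse events". Vital signs, an ECG and safety samples may be taken there.

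Among the reasons for withdrawal, Protocol 10.3 includes "Experience an AE that warrants premature withdrawal". Patients withdrawn early should have the Month 12/ET evaluations if possible. Protocol Table 2 gives those evaluations and the true Month 12 visit a single column. The SAP does not say where an early-termination value is shown.

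**The concern.** A by-visit, observed-case summary describes whoever attended that planned visit. The primary objective concerns the treated patients. The two can differ in three ways:

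- A test repeated or first taken at an unscheduled visit, often because something was abnormal, has no row.
- A patient who leaves the study contributes nothing to later rows.
- A value taken when a patient leaves early may appear in the Month 12 row, although it could date from the first weeks.

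No table title in SAP 4.1 indicates a summary that follows each patient across visits, such as the worst post-baseline value, a shift from Baseline, or a count beyond a cut-off. SAP 2.9.5 derives QTcF, but the text plans no outlier count for it.

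The SAP does take the worst occurrence per patient for adverse events, where the highest severity is reported. The other primary endpoints have nothing equivalent. In a study of about 12 patients, one patient is 1/12 = 8.3% of the evidence.

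**Working it through.** **No planned figure to reproduce.** SAP 2.13 says "This study is not powered for statistical significance. No sample size calculations were performed". The documents give no dropout rate and no SD for any safety parameter. What can be checked is the mechanism and its largest plausible size.

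**Inputs.** N = 12, from SAP 1.2 ("Approximately 12 NL patients (6-9 patients without ulceration and 3-6 patients with ulceration"). The number leaving, k = 1, 2 or 3, and the size of change, D, are assumptions.

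**Step 1: where each kind of record goes under SAP 2.14.**

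| Record | By-visit summary | Elsewhere |
|---|---|---|
| Planned visit, attended | Included; sets the minimum or maximum if extreme | Listing; AE table if it is an AE |
| Unscheduled visit | None | Listing; AE table if it is an AE |
| Planned visits after leaving | No value; n falls | None |
| Early termination | Not stated; may fall under Month 12 | Listing; AE table if it is an AE |

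**Step 2: effect of leavers on a mean.** Suppose k patients have change D at one visit and then leave, and all others have mean change 0.

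- Mean while they attend = kD/12.
- Observed-case mean after they leave = 0, with n = 12 − k.

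| k | Mean while attending, D = 30 | Mean while attending, D = 60 | Later mean (n) | Per-patient count |
|---|---|---|---|---|
| 1 | 30/12 = 2.5 | 60/12 = 5.0 | 0 (11) | 1/12 = 8.3% |
| 2 | 60/12 = 5.0 | 120/12 = 10.0 | 0 (10) | 2/12 = 16.7% |
| 3 | 90/12 = 7.5 | 180/12 = 15.0 | 0 (9) | 3/12 = 25.0% |

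A per-patient count keeps these patients at every data cut. The exact 95% upper limits for 1/12 and 2/12 are 38.5% and 48.4%, so even the count would be imprecise.

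**Step 3: extreme case in SD units.** Let the 12 changes be independent standard normal, and let exactly the k patients with the largest changes leave. The mean of all 12 is 0 in expectation, so the mean of those who remain is −(sum of the k largest expected order statistics)/(12 − k). For n = 12 the three largest are 1.629, 1.116 and 0.793.

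- k = 1: −1.629/11 = −0.148 SD
- k = 2: −(1.629 + 1.116)/10 = −2.745/10 = −0.274 SD
- k = 3: −(1.629 + 1.116 + 0.793)/9 = −3.538/9 = −0.393 SD

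A simulation of 400,000 sets of 12 gave −0.147, −0.273 and −0.392, in agreement. Rounded, the later means shift by 0.15, 0.27 and 0.39 SD. This is the outer case, because departure is tied perfectly to the size of change in the one parameter considered.

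**The case against.** The other side has a good deal in its favour.

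- **More than means is planned.** A reader might infer that the summaries are means alone. They are not: n shows attrition, and minimum and maximum show the most extreme patient at each visit. Frequency tables and full listings are also planned. This stands.
- **Adverse-event tables catch much of what matters.** A reader might infer that a marked abnormality seen only at an unscheduled visit appears in no table. Protocol 15.2.1 does not support that. It makes an abnormal result an adverse event when, for example, it leads to withdrawal or needs treatment or further evaluation, so investigator judgement is not the only route. Adverse events are themselves primary and counted per patient over the Safety Population, with a table of those leading to study discontinuation. This stands, but an adverse-event count is not a summary of how far laboratory, vital-sign or ECG values moved.
- **Stopping drug is not meant to be leaving the study.** Protocol 12.5 and SAP 1.2 keep such patients in, and Protocol 10.3 asks for evaluations on early withdrawal. This reduces the loss without removing it. Protocol 9.2.2.2 takes out patients who cannot tolerate the single tablet after 2 weeks, before the first planned post-baseline tests at Day 28. Protocol 19.5.2 takes out those who refuse treatment.
- **The endpoint is itself defined by visit.** The by-visit tables do match SAP 1.4.1 and should stay, and observed-case tables are usual in a small open-label study.
- **Repeats follow an original value.** If the first abnormal result came from a planned visit, it is already in that row. This is true for repeats, but not for tests first taken at an unscheduled visit to follow an adverse event.
- **Table shells are in a separate file.** Rows not visible here could exist, but the SAP text calls for none.

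**Conclusion.** This is a reporting gap in a primary endpoint. No computed result is wrong. The numeric laboratory, vital-sign and ECG summaries rest on planned visits and observed cases alone. Unscheduled values enter no by-visit row, leavers fall out of later rows, and early-termination values have no stated place. The existing safeguards limit the loss, but none gives a per-patient count or worst change over all treated patients.

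A reader might go further and infer that the later primary results will look safer than they were, by 0.15 to 0.39 SD. The documents do not support that. The range assumes normal changes and that the 1 to 3 leavers of 12 are exactly those with the largest changes. That cannot generally hold for many parameters at once, and an increase is not adverse for every parameter. An early-termination value placed under Month 12 could also move that row the other way. Nor is the rule about 4 of the first 6 patients a forecast of attrition: it is a trigger, and it pools dose modification with discontinuation. With no dropout rate or SD stated, the actual bias is unknown.

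The change should still be made before the analysis, because it is cheap and concerns the study's primary question.

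**What to change.** Keep the by-visit tables. In tables 14.3.5.1, 14.3.5.2, 14.3.6.1 and 14.3.6.2, for the Safety Population, add:

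1. Each patient's worst post-baseline value and worst change from Day 0, in the direction of concern for the parameter (highest and lowest where either matters), from planned, unscheduled and early-termination records.
2. The number of patients shifting from within to outside the laboratory reference range, and the number beyond cut-offs prespecified in the SAP for vital signs and QTcF. The denominator is dosed patients with any post-baseline value.

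In SAP 2.14 state that unscheduled and early-termination records enter these summaries, although they are assigned to no planned visit, and that early-termination values obtained before Month 12 are not shown in the Month 12 row.

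Protocol 9.2.2.2, 10.3, 12.5 and 19.5.2 differ on whether stopping drug means leaving the study, and must be reconciled.

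The cost is SAP wording and extra rows in four existing tables, from data already collected. One small downside is that a worst value taken over several visits is more extreme by chance, so the new rows should be read beside the by-visit ones.
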